5.8. Reports to be Generated at Interim and Final Database Lock

5.8.1. Report to be Generated at Interim Analysis

At the time of interim analysis, all randomized patients will have had the chance to complete Month 6 (Visit 10) in Study Period III. Analyses conducted at the interim analysis do not include any data from Study Period IV, unless otherwise specified. Efficacy/health outcome results are up to Month 6 data in SP III. Safety/protocol deviation results are based on all data during SP III.

For efficacy/health outcome analysis in SP III (continuous/binary outcomes using MMRM/GLIMMIX), overall (month 1-6) will be shown for treatment comparisons at the interim DBL instead of overall (month 1-12). They will be estimated as the main effect of treatment using Month 1 up to Month 6 data.

Disposition

- Patient Allocation by Investigator Site
- Summary of Patient Dispositions for Treatment Phase
- Listing of Subjects who discontinued for Treatment Phase or Post-Treatment Phase
- Listing of Patient Population by Treatment

Baseline Demographic

- Baseline Demographics and Disease Characteristics - Continuous Variables
- Baseline Demographics and Disease Characteristics - Categorical Variables
- Listing of Subjects Demographic

Efficacy/Health outcome

- Change from Baseline in the Number of Migraine Headache Days by 2 arms (CM120, CM240) using MMRM
- Change from Baseline in the Number of Migraine Headache Days by 2 arms (CM120, CM240) using MMRM (Figure)
- Descriptive Summary of Number of Migraine Headache Days (monthly raw values and change from baseline monthly values) by 6 arms (LY120/LY120, LY240/LY240, PLA/LY120, PLA/LY240, CM120, CM240)
- Descriptive Summary of Number of Migraine Headache Days (monthly raw values) by 6 arms (Figure)
- Descriptive Summary of Number of Migraine Headache Days (change from baseline monthly values) by 6 arms (Figure)
- Change from Baseline in the Number of Migraine Headache Days with Acute Medication Use by 2 arms (CM120, CM240) using MMRM
- Change from Baseline in the Number of Headache Days by 2 arms (CM120, CM240) using MMRM
- Distribution of Response Rates Based on Number of Migraine Headache Days by 2 arms (CM120, CM240) using GLIMMIX
- Distribution of Response Rates Based on Number of Migraine Headache Days by 2 arms (CM120, CM240) using GLIMMIX (Figure)
- Estimated Proportion of 50% Responders for Migraine Headache Days by 2 arms (CM120, CM240) using GLIMMIX
- Estimated Proportion of 75% Responders for Migraine Headache Days by 2 arms (CM120, CM240) using GLIMMIX
- Estimated Proportion of 100% Responders for Migraine Headache Days by 2 arms (CM120, CM240) using GLIMMIX
- Change from Baseline in Migraine-Specific Quality of Life Questionnaire - Role Function-Restrictive Domain Score by 2 arms (CM120, CM240) using MMRM
- Change from Baseline in Patient Global Impression - Severity Scores by 2 arms (CM120, CM240) using MMRM

Safety: AE

- Overview of Adverse Events
- Adverse Events Leading to Discontinuation
- Serious Adverse Events
- Adverse Events Related to Injection Sites Leading to Discontinuation
- Adverse Events Leading to Discontinuation for Upper Respiratory Tract Infections
- Treatment-Emergent Adverse Events Related to Injection Sites by Max Severity
- Treatment-Emergent Adverse Events (sort by Preferred Term)
- Listing of Adverse Events Leading to Discontinuation and Serious Adverse Events

Safety: Lab

- Abnormal Changes in Hepatic Laboratory Measures at Any Time
- Treatment-Emergent Abnormal Laboratory Measures at Any Time
- Listing of Subjects with abnormal Laboratory Results
- Listing of Subjects with abnormal Hepatic Laboratory Results

Safety: ECG

- Shift Table Summary of Qualitative ECG Abnormalities by Finding Category
- Summary of Qualitative ECG Abnormalities - From Baseline Normal to Post-Baseline Abnormal
- Change from Baseline to LOCF Endpoint in ECG Intervals and Heart Rate
- Treatment-Emergent Abnormalities for ECG Intervals and Heart Rate at Any Time
- Listing of Subjects with Treatment or Post-Treatment Emergent ECG findings
- Listing of Subjects with QRS ≥ 120 Milliseconds at Any Time
- Listing of Abnormal Qualitative ECG by Finding Category

Safety: Other

- C-SSRS summary and/or listing

Protocol Deviations

- Summary of Important Protocol Deviations in SP III
- Summary of Important Protocol Deviations in SP IV
- Listing of Important Protocol Deviations in SP III
- Listing of Important Protocol Deviations in SP IV

5.8.2. Report to be Generated at Final Database Lock

For the final database lock, all TFLs will be created. At the timing of the final database lock, all randomized patients will have had a chance to complete or discontinue 12 months of treatment period (Study Period III) and 4 months of the post-treatment period (Study Period IV.)

Analyses at final lock combined with some of the analysis from interim analysis will be used in the final CSR.

5.9. Clinical Trial Registry Analyses

Additional analyses will be performed for the purpose of fulfilling the Clinical Trial Registry (CTR) requirements. These analyses will be the responsibility of the Sponsor.

Analyses provided for the CTR requirements include the following:

A summary of AEs will be provided as a dataset, which will be converted to an XML file. Both SAEs and “Other” AEs are summarized: by treatment group, by MedDRA PT.

- An AE is considered “Serious” whether or not it is a TEAE.
- An AE is considered in the “Other” category if it is both a TEAE and is not serious. For each SAE and “Other” AE, for each term and treatment group, the following are provided:
 - the number of participants at risk of an event
 - the number of participants who experienced each event term
 - the number of events experienced
- Consistent with www.ClinicalTrials.gov requirements, “Other” AEs that occur in fewer than 5% of patients in every treatment group may not be included if a 5% threshold is chosen.
- AE reporting is consistent with other document disclosures for example, the CSR, manuscripts, and so forth.

6. References

- [ICHD-3] Headache Classification Committee of the International Headache Society (IHS). The International Classification of Headache Disorders, 3rd edition (beta version). *Cephalalgia*. 2013;33(9):629-808.
- Kalali A. Patient satisfaction with, and acceptability of, atypical antipsychotics. *Curr Med Res Opin*. 1999;15(2):135-137.

Leo Document ID = d7ef76d7-4e45-49ca-8679-814615985d66

Approver: PPD

Approval Date & Time: 16-Jul-2019 01:26:46 GMT

Signature meaning: Approved

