
 • To evaluate the long-term effect of galcanezumab on quality of life • To evaluate patient satisfaction with medication • To evaluate safety and residual treatment effect during the post-treatment follow-up period 	
 • Patient’s global impression of improvement as measured by PGI-I • Mean change from baseline in the number of monthly migraine headache days requiring medication for the acute treatment of migraine headache • Mean change from baseline to endpoint in the evaluation of the MIDAS total score and individual items • Mean change from baseline to endpoint in the MSQ (v2.1) total score and individual domains • Descriptive summary at each visit for HCRU and employment status • Satisfaction with medication using the PSMQ-M • Analysis of safety parameters • Time to first loss of response (when patient no longer meets 50% response criteria) during the post-treatment follow-up phase

Abbreviations: ADA = anti-drug antibodies; CGRP = Calcitonin gene-related peptide; C-SSRS = Columbia Suicide Severity Rating Scale; ECGs = Electrocardiograms; HCRU = Health Care Resource Utilization; MIDAS = Migraine Disability Assessment test; MSQ (v2.1) = Migraine Specific Quality of Life Questionnaire version 2.1; PGI-I = Patient Global Impression of Improvement; PGI-S = Patient Global Impression of Severity; PSMQ-M = Patient Satisfaction with Medication Questionnaire-Modified; TEAEs = treatment-emergent adverse events.

Table CGAP. 4.2 Migraine and Headache Endpoint Definitions

Diagnosis	Definition/Criteria
Migraine headache (patients with EM only)	
A headache, with or without aura, of ≥ 30 minutes duration with both of the following required features (A and B):
 
A. At least 2 of the following headache characteristics:
 
 • Unilateral location • Pulsatile quality • Moderate or severe pain intensity • Aggravation by or causing avoidance of routine physical activity 
AND
 
B. During headache at least 1 of the following:
 
 • Nausea and/or vomiting • Photophobia and phonophobia 
(Definition adapted from the IHS ICHD-3 beta)

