5.5.1.4. Baseline and Post-Baseline Definition

[Table CGAP. 5.4](#) describes the rules for determining the patient population and baseline and post-baseline observations for each study phase and type of analysis. When “last of Visit x-x” is used in the table, the last nonmissing observation obtained in the visit interval will be used.

Table CGAP. 5.4 Patient Population with Baseline and Post-Baseline Definitions by Study Period and Type of Analysis

Study Period/Analysis	Patient Population	Baseline Observation	Post-baseline Observation(s)
Study Period III			
Efficacy analyses	ITT Population with a baseline and at least 1 post-baseline observation	Visit 3	All Visits 3.01–16
Mean change from baseline in the number of migraine headache days	PPS Population with a baseline and at least 1 post-baseline observation	Visit 3	All Visits 3.01–16
Quality of Life analyses	ITT Population with a baseline and at least 1 post-baseline observation	Visit 3	All Visits 3.01–16
TEAEs	Safety Population	EM: CGAN Visit 1 – CGAP Visit 3 CM: All Visits 1–3. Pre-existing condition that is still ongoing at Visit 1 should be evaluated as baseline values.	All Visits 3.01–16
Serious Adverse Events, Discontinuations due to Adverse Events	Safety Population	NA	All Visits 3.01–16
C-SSRS categorical analyses	Safety population with a baseline and at least 1 post-baseline C-SSRS assessment	EM: Recent History: CGAP Visit 3 All Prior History: All CGAN Visits 1-12 including lifetime ^a CM: Recent History: All CGAP Visits 1–3 excluding lifetime ^a	All Visits 3.01–16

Study Period/Analysis	Patient Population	Baseline Observation	Post-baseline Observation(s)
		All Prior History: All CGAP Visits 1 – 3 including lifetime ^a	
C-SSRS categorical analyses for improvement	Safety population with a baseline and at least 1 post-baseline C-SSRS assessment	EM: Visit 3 CM: Last of CGAP Visit 1-3.	Last of 3.01–16
Treatment emergent abnormal laboratory values	Safety Population with normal laboratory values at all nonmissing baseline visits (with respect to direction being analyzed) and who have at least 1 post-baseline observation	EM: Visit 3 CM: All Visits 1–3	All Visits 3.01–16
Treatment emergent immunogenicity	Safety Population. ADA follow-up cohort (See Section 5.5.12.1.6)	EM (LY120/LY120, LY240/LY240): CGAN Visit 3 EM (PLA/LY120, PLA/LY240): CGAP Visit 3 CM: Visit 3	All Visits 3.01–16

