5.5.12.1.1. Adverse Events

Treatment-emergent adverse events are defined as the reported AEs that first occurred or worsened during the post-baseline phase compared with the baseline phase. Pre-existing condition that is still ongoing at Visit 1 for CM patients should be evaluated as baseline values. For each TEAE, the severity level of the event (mild, moderate, or severe) will be determined by patient or physician opinion. The MedDRA Lowest Level Term (LLT) will be used in the treatment emergent computation. For each LLT, the maximum severity at baseline will be used as the baseline severity. If the maximum severity during post-baseline is greater than the maximum baseline severity, the event is considered to be treatment-emergent for the specific post-baseline period. For each patient and TEAE, the maximum severity for the MedDRA level being displayed (PT, High Level Term, or SOC) is the maximum post-baseline severity observed from all associated LLTs mapping to that MedDRA level.

Follow-up emergent adverse events (post-treatment emergent adverse events) are defined similarly. They are events that first occurred or worsened during the follow-up period (Study Period IV) when compared to the baseline (SP I, SP II, and SP III). Pre-existing condition that is still ongoing at Visit 1 for CM patients should be evaluated as baseline values. (See detail definitions in [Table CGAP. 5.4](#))

For events that are gender-specific, the denominator and computation of the percentage will include only patients from the specific gender.

Following summary will be created:

- Overview of AE (SP III)
- TEAEs (SP III)
 - By PT by decreasing frequency
 - By SOC/PT
 - By maximum severity/PT
- FEAEs (SP IV)
 - By PT by decreasing frequency
 - By SOC/PT
 - By maximum severity/PT
- TEAEs by considered to be related to investigational product by investigator (SP III)
- Treatment Emergent Adverse Events that started on Treatment phase and Continuing in Post-Treatment Phase (SP III, SP IV combined)
- SAEs (SP III, SP IV separately)
- AEs leading to discontinuation (SP III, SP IV separately)

Following tables are created by 6 arms (with LY_ALL) without statistical tests:

- TEAEs (SP III) by SOC/PT
- TEAE by considered to be related to investigational product by investigator (SP III)

Listing of Subjects with TEAE or FEAE (SP III, SP IV combined) will be created.

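### As written, the registry rule for non-serious adverse events (SAP 5.9) admits TEAEs only, so it leaves out events that first emerge in follow-up, and it names no period or population for the number at risk

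*SAP*

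**What the plan says.** **Registry rules (SAP 5.9).** A non-serious event goes into the *Other* "category if it is both a TEAE and is not serious". An event counts as serious "whether or not it is a TEAE". For each term and treatment group the dataset gives "the number of participants at risk of an event", but no population or study period is named. The section also states: "AE reporting is consistent with other document disclosures for example, the CSR, manuscripts, and so forth". If a 5% threshold is chosen, *Other* terms below 5% in every treatment group may be left out.

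**Event classes (SAP 5.5.12.1.1 and Table CGAP. 5.4).** TEAEs are events that "first occurred or worsened during the post-baseline phase compared with the baseline phase". Table CGAP. 5.4 lists them under SP III only, on the Safety Population, with post-baseline window "All Visits 3.01–16". FEAEs have their own paragraph, in which the treatment period is the last of three baseline periods: "They are events that first occurred or worsened during the follow-up period (Study Period IV) when compared to the baseline (SP I, SP II, and" […]. In Table CGAP. 5.4 they sit under SP IV, on the Post-treatment Population, with window Visits 16.01 to 18.

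**Objective (SAP Table CGAP. 4.1).** One secondary objective is "To evaluate safety and residual treatment effect during the post-treatment follow-up period". Section 5.4 of the protocol addendum gives safety during wash-out as the reason for the 4-month follow-up.

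**The concern.** The registry rule uses one of the SAP's two emergence labels and does not mention the other. A non-serious event that first appears or worsens in SP IV is an FEAE. It is not serious and, by Table CGAP. 5.4, it is not a TEAE, so neither registry rule admits it. A serious event with the same onset date meets no such filter.

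The public record could therefore show no non-serious follow-up events in a trial that makes follow-up safety an objective, while the study report shows them. Because 5.9 names no period or population, a programmer building the dataset would also have to guess which denominator applies.

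**Working it through.** **1. Is the TEAE label confined to SP III?**

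| Place in SAP | Treatment of the two classes |
|---|---|
| 5.4.4 | FEAEs in SP IV named as a safety endpoint beside TEAEs |
| Table CGAP. 5.4 | TEAEs: SP III, Safety Population. FEAEs: SP IV, Post-treatment Population |
| 5.5.12.1.1 | Separate tables for TEAEs (SP III) and FEAEs (SP IV), and one listing that names both; refers to Table CGAP. 5.4 for detailed definitions |
| 5.5.1 | Equates post-treatment emergent with follow-up emergent, not with treatment-emergent |
| 5.9 | Uses TEAE only; FEAE does not appear |

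The rule therefore sorts events as follows.

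| Event | Serious rows | *Other* rows |
|---|---|---|
| Non-serious, emerges in SP III | no | yes |
| Non-serious, emerges in SP IV | no | no |
| Serious, emerges in SP III | yes | no |
| Serious, emerges in SP IV | yes, unless a time window is applied (none is stated) | no |

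**2. Length of the uncovered window.** The schedule puts Visit 16 at Month 12 and Visit 18 at Month 16. 16 − 12 = 4 months, or 60 + 60 = 120 days, as the SAP states. That is 4/16 = 25% of planned observation for a patient who finishes both periods.

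**3. Is the window drug-free?** The addendum gives about 5 half-lives in 5 months, so a half-life of about 1 month. Its wash-out figure is reproduced: 1 − 0.5^5 = 0.969, about 97%. The last dose is at Visit 15 (Month 11). The fraction of the last-dose concentration remaining is 0.5^1 = 50% at Visit 16, 0.5^3 = 12.5% at Visit 17 and 0.5^5 = 3.1% at Visit 18. Early SP IV is not drug-free; late SP IV nearly is.

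**4. Illustration of the omitted share.** The documents give no FEAE rate and no SP IV entry rate, so every input here is an assumption. Let p be the 12-month risk of a first event, f the fraction followed into SP IV, and r the SP IV onset rate relative to SP III.

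- Extra patients affected in SP IV: e = f × (1 − p) × [1 − (1 − p)^(r/3)]
- Omitted share: e / (p + e)

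| p | f | r | e | Omitted share |
|---|---|---|---|---|
| 5% | 1 | 1 | 1.6% | 24% |
| 10% | 1 | 1 | 3.1% | 24% |
| 20% | 1 | 1 | 5.7% | 22% |
| 10% | 0.7 | 1 | 2.2% | 18% |
| 10% | 1 | 0.5 | 1.6% | 14% |
| 10% | 0.7 | 0.5 | 1.1% | 10% |
| any | any | 0 | 0 | 0% |

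The value f = 0.7 borrows the assumed 30% non-completion of treatment (SAP 5.2), which is not an SP IV entry rate.

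**5. Denominator.** With 70% to 100% entering SP IV, a CM arm of 30 has 21 to 30 at risk, so one patient is 4.8% to 3.3%. An EM arm of 120 has 84 to 120, so one patient is 1.2% to 0.8%. The choice of population matters modestly, and most in the CM arms.

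**6. The 5% threshold on separate SP IV rows.** With r = 1, the 4-month risk is 1 − (1 − p)^(1/3): 1.7%, 3.5% and 7.2% for p = 5%, 10% and 20%. It reaches 5% only when p = 1 − 0.95^3 = 14.3%. Most SP IV terms would then be expected below the threshold, although two patients in one CM arm (2/30 = 6.7%) would keep a term.

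**The case against.** The strongest reply is that the SAP does not use the TEAE label strictly. The general definition speaks of a post-baseline phase. Section 5.5.12.1.1.3 asks for TEAEs of upper respiratory infection in both SP III and SP IV. The suicidality, vital sign and ECG sections also apply treatment-emergent wording to SP IV. On that reading TEAE in 5.9 could already cover follow-up, and the consistency sentence could be taken as an instruction to align the registry with the CSR. This shows that the label is loose and that a sensible programmer might include FEAEs. It does not override Table CGAP. 5.4, to which 5.5.12.1.1 refers for the detailed definitions, and it would make the separate FEAE class redundant.

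Second, the consequence is limited. FEAEs are tabulated by preferred term, by system organ class and by maximum severity, and they are listed. The follow-up safety objective is met in the CSR. This stands in full.

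Third, constant risk after dosing stops is generous. No injection is given after Visit 15, so events caused by a new injection cannot arise in SP IV, and concentration is about one-eighth of the last-dose level or less from Visit 17 on. This also stands, so the 18 to 24% is an illustration and not an estimate.

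A reader might also infer that serious and *Other* events share one number at risk, or that serious events are counted at any time, including before the first dose. Section 5.9 says neither. It names no denominator population for either class, and dropping the TEAE condition for serious events sets no time window. Elsewhere the SAP summarises serious events for SP III and SP IV separately, on different populations.

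**Conclusion.** The point holds in a limited form. Read with Table CGAP. 5.4 and Section 5.5.12.1.1, the *Other* rule leaves non-serious follow-up-emergent events out of the registry table, while serious events face no emergence filter. This is hard to square with the consistency statement in 5.9. The missing period and population for the number at risk is a second, related gap.

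The conclusion rests on taking Table CGAP. 5.4 as the governing definition of a TEAE. It does not support a claim that a known number or proportion of events is lost, because the documents give no follow-up event rate. The range of 18 to 24% of affected patients needs constant onset risk; halving the SP IV rate at p = 10% gives 10 to 14%. Nor does it support a claim that follow-up safety goes unreported, or that any primary or secondary analysis changes. Only the public registry record is affected. Priority: low.

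**What to change.** In SAP 5.9:

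- Define *Other* as a non-serious TEAE (SP III) or a non-serious FEAE (SP IV).
- Show SP III and SP IV as separate sets of rows and state the number at risk for each: Safety Population for SP III and Post-treatment Population for SP IV, as in Table CGAP. 5.4. Note that Section 5.5.1.3 assigns arms by modal treatment in the first and by randomised treatment in the second.
- Assign each serious event to the period in which it starts, so that serious and *Other* rows cover the same windows.
- If the 5% threshold is used, say whether it applies to each period separately or to the term across both. Applied to the SP IV rows alone, it could remove most of what the change adds.

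FEAEs are already derived for the CSR, so the cost is a few sentences of SAP text, some extra registry rows and a longer table.
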